13.3.3 Interim analyses

No interim analysis will be done

13.3.4 Safety analysis

Safety issue is expected to be small and will be describe using number, frequency and 95% CI.

13.3.5 Deviation(s) from the original statistical plan

We refer to the master protocol.

13.4 HANDLING OF MISSING DATA AND DROP-OUTS

We refer to the master protocol.

13.5 QUALITY ASSURANCE AND CONTROL

13.6 DATA HANDLING AND RECORD KEEPING / ARCHIVING

We refer to the master protocol.

14. DATA MANAGEMENT

We refer to the master protocol.

15. MONITORING

We refer to the master protocol.

16. AUDITS AND INSPECTIONS

We refer to the master protocol.

17. CONFIDENTIALITY, DATA PROTECTION

We refer to the master protocol.

18. STORAGE OF BIOLOGICAL MATERIAL AND RELATED HEALTH DATA

Samples used for diagnostic at the IMV in Zürich will be stored for 5 years.

19. PUBLICATION AND DISSEMINATION POLICY

All trials that are set-up within the trial platform and results from sub-studies will be published (also negative results or if a trial has to be discontinued) in peer-reviewed journal publications. We intend to make this sub-protocol available on clinicaltrials.gov. Authorship to publications will be granted according to the rules of the International Committee of Medical Journal Editors (ICMJE).

20. FUNDING AND SUPPORT

This COVERALL substudy-3 is funded by Moderna (European/Swiss headquarters: [name], Switzerland). The set-up of the trial platform was funded by the Swiss National Science Foundation (grant # 31CA30_196245). The Swiss HIV Cohort Study (SHCS) and the Swiss Transplant Cohort Study (STCS) are funded by the Swiss National Science Foundation (SHCS: grant # 177499 and # 201369, STCS: grant # 33CS30_177522). Moderna had the possibility to read and approve the study protocol before the study was started. Futhermore Moderna will have the right to review the results manuscript before it will be submitted for publication. Otherwise, the funders will have no role in study design, data collection and analysis, decision to publish, or preparation of the manuscript.

21. INSURANCE

We refer to the master protocol.

23. APPENDICES

Not applicable

PI	Principal Investigator
RBD	Receptor binding domain
RECORD	REporting of studies Conducted using Observational Routinely-collected Data
SARS-CoV-2	Severe acute respiratory syndrome coronavirus 2
SDV	Source Data Verification
SHCS	Swiss HIV Cohort Study
SOP	Standard Operating Procedure

SPC	Summary of product characteristics
SPIRIT	Standard Protocol Items: Recommendations for Interventional Trials
STCS	Swiss Transplant Cohort Study
SUSAR	Suspected Unexpected Serious Adverse Reaction
TMF	Trial Master File

STUDY SYNOPSIS

Randomised controlled trials to assess approved SARS-CoV-2 vaccines in immunocompromised patients: First sub-protocol for a pilot trial comparing the mRNA vaccines Comirnaty® and Covid-19 mRNA Vaccine Moderna®

Brief Title: Immunocompromised Swiss Cohorts Based Trial Platform,
Acronym: COVERALL (COrona VaccinE tRIAL pLatform)

Rationale: A new highly contagious corona virus SARS-CoV-2 has emerged in late 2019 in Wuhan, China, and caused in a two-month period a pandemic with the highest disease burden in elderly and people with pre-existing medical conditions. After nearly one year into the epidemic over 0.5 million infections, over 21'000 hospitalisations, and over 82000 deaths due to Sars-CoV-2 have been recorded in Switzerland (January 21, 2021).

Since January 12, 2021 two mRNA vaccines against Sars-CoV-2 by Pfizer / BioNTech (Comirnaty®) and COVID-19 mRNA Vaccine Moderna® by Moderna have been licensed in Switzerland and roll-out of vaccines has started.

In phase III licensing trials of both vaccines, vaccine efficacy of 95% and 94% were found and both vaccines appeared to be safe. However, few individuals with HIV infection were included in both trials and no solid organ recipients were enrolled in the trials.

Data on vaccine efficacy, induced immune response and safety in immunocompromised individuals with chronic HIV infection or solid organ transplantation is missing. We intend to close this information gap with a pilot trial, which represents the first-sub-study trial of the established trial platform that is linked and nested into the existing prospectively collected data structure of the Swiss HIV Cohort Study (SHCS) and the Swiss Transplant Cohort Study (STCS).

Objectives and Endpoints:

To investigate the operability of a platform trial that is nested into two existing cohort studies and compare immune response, safety and clinical efficacy of the first two mRNA vaccines (Comirnaty® by Pfizer / BioNTech and COVID-19 mRNA Vaccine Moderna®, by Moderna) in immune compromised patients in the Swiss HIV and Swiss Transplant Cohort studies.

Feasibility endpoints:

We refer to the master protocol

Immunological endpoints (primary endpoint)

- Immune response (pan-Ig antibodies against the receptor binding domain (RBD) in the S1 subunit of the spike protein (pan-Ig anti-S1-RBD) of SARS-CoV-2.
- Newly PCR-confirmed asymptomatic SARS-CoV-2 infection

Clinical Endpoints

- Newly PCR-confirmed symptomatic SARS-CoV-2 infection
- Severe COVID-19 infection, hospitalization due to COVID-19 or death
- COVID-19 burden of diseases (BOD)
- Patient reported asymptomatic or symptomatic infections of household members.

Safety endpoints

- Adverse events from vaccines and
- Serious adverse events

Overall Design:

Multicenter randomised controlled, open-label, 2-arm sub-study pilot trial of a platform trial nested in two national cohorts

Number of Participants enrolled:

Eligible individuals are screened and flagged in both cohorts according to priority vaccination recommendations by the BAG. We will randomise 380 patients from both cohorts (recruitment of

patients from the Swiss Transplant Cohort Study will be limited to kidney and lung transplant recipients. These patients will be randomised to vaccination with Comirnaty® or the COVID-19 mRNA Vaccine Moderna®.

Intervention Groups and Duration:

Participants of the Swiss HIV Cohort and Swiss Transplant Cohort Studies with informed consent and no exclusion criteria will be centrally randomised via the trial platform to vaccination with mRNA vaccines COVID-19 mRNA Vaccine Moderna® or Comirnaty® (Pfizer / BioNTech) at day 0 with booster vaccines at day 21 and day 28, respectively. Antibodies against Sars-Cov-2 will be measured at baseline and 12 weeks with the Elecsys® anti-SARS_CoV_2 S and N (Roche Rotkreuz Switzerland) and ABCORA2.0 (IMV) assays. Vaccine related AE will be assessed at 12 weeks. SAE and asymptomatic or symptomatic Sars-Cov-2 infection (PCR confirmed) and hospitalisation, ICU admission, or death from any cause will be recorded at 48 weeks within the clinical trial platform and by routine cohort data collection.

STUDY SCHEDULE

	STUDY PERIOD					
	Eligibility	Enrolment, randomisation & vaccination	Post-randomisation			
TIMEPOINT	Approximately -12 weeks	Day 0	Week 4	Week 12 (±7 days)	Week 48 (±7 days)	Continuous follow-up in the frame of the cohort
ENROLMENT:						
Eligibility screen ^a	X ^a					
Eligibility assessment	X					
Informed consent		X ^a				
Allocation		X ^b				
INTERVENTIONS:						
Intervention COVID-19mRNA Vaccine Moderna®		X	X			
Control Comirnaty® (Pfizer/BioNTech vaccine)		X	X			
ASSESSMENTS:						
BASELINE VARIABLES (will be exported from routine cohort data) Baseline blood sample	X					
IGG neutralizing antibodies post randomisation but prior to vaccination		X				
CLINICAL OUTCOMES:						
- Immune response IgG neutralizing antibodies	X ^e	X ^e		X ^c		
- Newly confirmed asymptomatic SARS-CoV-2 infection				X ^c	X ^{c,d}	X ^d
-Newly confirmed symptomatic SARS-CoV-2 infection				X ^c	X ^{c,d}	X ^d
- Severe COVID-19 infection with respiratory failure, evidence of shock, organ failure, admission to ICU, or death				X ^c	X ^{c,d}	X ^d
- Adverse events from vaccines				X ^c		
-Serious adverse events			X ^{c,d}	X ^c	X ^{c,d}	X ^d
- PCR confirmed symptomatic infections of household members				X ^c	X ^{c,d}	X ^d

^aContinuous assessment and selection from routinely collected cohort data

^bEnrolment and concealed allocation of patients with informed consent will be performed during the same visit when the study is explained to the patient, or, if preferred, during a separate arranged study visit.

^cAssessed in separate data entry form for the trial

^d Assessed by routine data collection from cohort data base

^eBaseline blood samples will be taken from previous cohort visits (no longer than 6 months) or during cohort and randomisation visits at day 0.

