5.2 Clinical Outcomes

The clinical effectiveness endpoints are (according to FDA recommendations for phase III Covid-19 vaccine licensing trials (14)) the following:

- Newly PCR-confirmed asymptomatic COVID-19 infection (identified by the presence of anti-SARS-CoV-2 nucleocapsid antibodies or SARS-Cov-2 PCR or rapid antigen test) and no related symptoms [(i.e. fever or chills, cough, shortness of breath or difficulty breathing, fatigue, muscle or body aches, headache, new loss of taste or smell, sore throat, congestion or runny nose, nausea or vomiting, and diarrhea)] at any time point in within 48 weeks following randomisation.
- Newly PCR-confirmed symptomatic COVID-19 infection with at least one of the following symptoms (i.e. fever or chills, cough, shortness of breath or difficulty breathing, fatigue, muscle or body aches, headache, new loss of taste or smell, sore throat, congestion or runny nose, nausea or vomiting, and diarrhea at any time point in within 48 weeks following randomisation
- severe COVID-19 infection with respiratory failure, evidence of shock (as diagnosed by a treating physician), clinically significant acute renal, hepatic, or neurologic dysfunction; admission to an intensive care unit; and death at any time point in within 48 weeks following randomisation.
- COVID-19 burden of diseases (BOD), a composite of the above endpoints. The BOD is will be scored as by using 0 for no COVID-19, 1 for non-severe COVID-19, and 2 for severe COVID-19.

An additional clinical effectiveness endpoint is patient reported asymptomatic or symptomatic infections of household members.

All clinical outcomes will be measured in the trial database during a follow-up period of 48 weeks after randomisation and vaccination.

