7.1 Eligibility criteria

Inclusion and exclusion criteria as defined in the master protocol:

Inclusion criteria:

- All patients with either a chronic HIV infection or recipients of solid organs registered with informed consent from the SHCS and STCS cohorts aged ≥ 18 years
- Patients with solid organ transplantation of lungs or kidneys at least one month post-transplantation with a prednisone dose of 20mg or less.
- Additional consent for participation in the pilot trial
- Covid-19 vaccination recommended by treating physician

Exclusion criteria:

- Pregnancy
- Acute symptomatic SARS-CoV-2 infection, influenza or other acute respiratory tract infection
- Known allergy or contra-indications for vaccines or any vaccine components
- Any emergency condition requiring immediate hospitalization for any condition
- Patients with previous PCR documented SARS-CoV-2 infection and, or documented antibodies less than 3 months prior to randomisation
- Patients with solid organ transplantation (lung or kidney) with the following conditions:
 - Solid organ transplant recipients less than one month post-transplantation
 - Solid organ transplant recipients with the use of T-cell depleting agents in the last 3 months (i. e induction treatment in standard risk or high-risk immunological situation or rejection treatment).
 - Solid organ transplant recipients with the need of pulse corticosteroids (>100 mg prednisone or equivalent) in the last 1 month or rituximab in the last 6 months
 - Solid organ transplant recipients with the need of any kind of chemotherapy treatment

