9.2.2 Assessment of immunological endpoints

We will assess pan-IgG anti S (RBD) (quantitative) and anti- N antibodies (qualitative) with the commercial Elecsys® Anti-SARS-CoV-2 tests at baseline and at 12 weeks following randomisation and vaccination (primary immunological endpoint).

We will assess SARS-CoV-2-binding antibody responses of the participants by analyzing the IgM, IgA and IgG responses to a wider range of SARS-CoV-2 proteins (S1, S2, RBD and N using an in-house method (ABCORA2.0) established at the Institute of Medical Virology (IMV), UZH (secondary immunological endpoint). The ABCORA 2.0 test allows for a parallel assessment of IgG, IgM and IgA reactivity to multiple antigens enabling a high-dimensional temporal resolution of antibody responses and a dissection between humoral responses to an infection and vaccination. We expect that the ABCORA2.0 antibody test will be more sensitive than the Elecsys® Anti-SARS-CoV-2 S antibody test.

Patients will be invited to see their treating physician 12 weeks after randomisation (see Study schedule). During baseline and follow-up visits this visit a blood sample will be taken (EDTA blood (2 x 7.5 ml)) and assessed for the above listed antibodies:

- 1ml for Elecsys® Anti-SARS-CoV-2 N and S tests (performed locally at each laboratory)
- 2ml EDTA Plasma for ABCORA 2.0 test (performed at IMV, UZH)

EDTA blood should be processed within 24h and EDTA plasma should be stored at -20°C. For ABCORA 2.1 antibody measurements plasma samples will be collected at each center and a collective shipment will be sent after baseline and at 12 weeks after randomisation and vaccination to the IMV, UZH. One sample will be stored according to SHCS and STCS protocols for later eventual analyses at the centers of University Hospital Zurich.

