9.2.3 Assessment of clinical endpoints

Patients are informed to contact center physicians in case an asymptomatic or symptomatic SARS-Cov-2 infections was diagnosed outside the settings of participating cohort centers. Clinical endpoints will be assessed at 12 and 48 weeks, and during each cohort visits, that fall in between the trial specific visit dates.

- Newly PCR-confirmed asymptomatic Covid-19 infection (identified by the presence of anti-SARS-CoV-2 nucleocapsid antibodies, or PCR or rapid antigen test) and no related symptoms [(i.e. fever or chills, cough, shortness of breath or difficulty breathing, fatigue, muscle or body aches, headache, new loss of taste or smell, sore throat, congestion or runny nose nausea or vomiting, and diarrhea)] at any time during the 48 weeks of follow-up

During all visits at the trial centres (study specific at 12 and 48 weeks, as well as cohort visits) a PCR SARS-COV-2 test will only be conducted if the treating physician would also conduct such a test during clinical routine (e.g. exposure to infected individual). PCR tests done in between independently will be recorded with dates and results. In case of a positive test result, physicians will check for symptoms and patients will be followed-up according to clinical routine and physicians' judgement.

- Newly PCR-confirmed symptomatic Covid-19 infection with at least one of the following symptoms (i.e. fever or chills, cough, shortness of breath or difficulty breathing, fatigue, muscle or body aches, headache, new loss of taste or smell, sore throat, congestion or runny nose nausea or vomiting, and diarrhea) at any time during the 48 weeks of follow-up

During all visits at the trial centres (study specific at 12 and 48 weeks, as well as cohort visits) a PCR SARS-COV-2 test will only be conducted if the treating physician would also conduct such a test during clinical routine (e.g. COVID-19 related symptoms; exposure to infected individual). In case of a positive test result, physicians will check for symptoms and patients will be followed-up according to clinical routine and physicians' judgement.

- Severe COVID-19 infection with respiratory failure, evidence of shock (as diagnosed by a treating physician), clinically significant acute renal, hepatic, or neurologic dysfunction; admission to an intensive care unit; or death at any time during the 48 weeks of follow-up.

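### A stored baseline sample up to 6 months old lets silent infections before randomisation be counted as new asymptomatic infections at week 12

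*Combined protocol and SAP*

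**What the plan says.** All references are to the first sub-protocol (Combined protocol and SAP) unless stated otherwise.

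- **Study schedule, footnote e:** baseline "blood samples will be taken from previous cohort visits (no longer than 6 months) or during cohort and randomisation visits at day 0". The footnote is attached to the immune-response row in both the eligibility and the Day 0 columns. It does not say from which date the 6 months are counted.
- **Same table, separate row ticked at Day 0, without footnote e:** "IGG neutralizing antibodies post randomisation but prior to vaccination".
- **Section 9.2.2:** "During baseline and follow-up visits this visit a blood sample will be taken". Stored samples are not mentioned as a source of baseline serology. Anti-S and anti-N are measured "with the commercial Elecsys® Anti-SARS-CoV-2 tests at baseline and at 12 weeks following randomisation and vaccination".
- **Section 5.2 (and 9.2.3):** a new asymptomatic infection in the 48 weeks after randomisation may be "identified by the presence of anti-SARS-CoV-2 nucleocapsid antibodies or SARS-Cov-2 PCR or rapid antigen test". The burden-of-disease score is a composite of the infection endpoints.
- **Section 9.2.3:** at study visits a PCR "test will only be conducted if the treating physician would also conduct such a test during clinical routine".
- **Section 7.1, exclusion:** "Patients with previous PCR documented SARS-CoV-2 infection and, or documented antibodies less than 3 months prior to randomisation".
- **Section 11.4.3:** the primary comparison is presence of anti-S antibody by arm. Clinical outcomes are reported as frequencies and percentages.

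**The concern.** An infection can be called new only if the baseline sample shows that it was absent when follow-up began. Footnote e allows that sample to predate Day 0 by months. A patient infected silently in the interval has a negative stored sample. Such a patient passes the exclusion criterion, because nothing was documented, and is anti-N positive at week 12. Since PCR is not systematic, paired serology carries much of the silent case finding, and nothing else would date the infection correctly.

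Two things are at stake. First, infections that neither vaccine could have influenced enter a stated endpoint and the burden-of-disease composite. Second, one trial may mix patients whose serological observation window is 12 weeks with patients whose window is up to about 38 weeks (26 + 12), with no rule to tell them apart.

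**Working it through.** **1. What the passages allow, side by side.** Footnote e offers a stored sample or a Day 0 sample as alternatives. The separate schedule row and section 9.2.2 describe a sample at the visit itself. A site could follow either and be compliant, so the text does not guarantee a Day 0 sample for everyone.

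**2. Share of conversions that predate randomisation.**

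Inputs: the follow-up window of 12 weeks (section 9.2.2) and the sample age L. The schedule labels its eligibility column as about 12 weeks before Day 0, and footnote e allows up to 6 months (26 weeks). Assumptions: the infection rate is constant, the 6 months run back from randomisation, and a new infection means anti-N negative at baseline and positive at week 12.

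Share = L / (L + 12)

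- Day 0 sample: 0 / 12 = 0%
- L = 12 weeks: 12 / 24 = 50%
- L = 13 weeks: 13 / 25 = 52%
- L = 26 weeks: 26 / 38 = 68%

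These are shares of serological conversions, not of patients. Section 3.7 says that daily deaths in December 2020 were high and had since fallen. If infections followed the same course, a look-back covering that period would give a larger share than the constant rate does.

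**3. Number of patients.** Let q be the proportion with an undocumented infection in the gap and only a stored sample. The count is 380 × q: 3.8 at q = 1%, 7.6 at 2% and 19 at 5%. These values of q are assumptions. The documents give no incidence, no proportion using stored samples and no proportion of infections left undocumented.

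**4. Effect on the infection endpoint.** If a and b are the true proportions newly infected in the two arms and m is the misdated proportion, equal in expectation by randomisation, the observed ratio is (a + m) / (b + m). This lies closer to 1 than a / b. The absolute difference stays about a − b, with more noise. No spurious difference between arms is created.

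**5. Effect on the primary comparison.** The plan's sample size (section 11.2) reproduces: with 90% in both arms, a 10-point margin, one-sided 0.025 and 90% power,

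n = (1.960 + 1.282)² × (0.09 + 0.09) / 0.10² ≈ 189.2, so 190 per arm and 380 in total (power 90.1%).

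Now suppose that a proportion q is anti-S positive at week 12 through earlier infection, whatever the vaccine does. The observed rate is p + (1 − p)q. At q = 5% and true rates of 90% and 80%, this gives 0.905 and 0.810. The difference is −9.5 instead of −10.0 points, and the one-sided type I error is 3.4% instead of 2.5%. The date of the baseline sample appears nowhere in this calculation. The shift comes from the earlier infection itself and is the same with a Day 0 sample, because section 11.4.3 does not use baseline status.

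**The case against.** - **The stored sample may serve screening only, with Day 0 blood still drawn.** This is a coherent reading of the separate Day 0 row. It is not secured, because footnote e is also attached to the Day 0 column and is worded as an alternative. What stands is that this is a contradiction to reconcile, not a settled plan to use old samples.
- **The exclusion removes recent infections.** It removes documented ones, so the point is limited to undocumented infections.
- **No passage states a negative-to-positive rule for anti-N.** This is correct, and step 2 assumes one. But calling an infection new presupposes a baseline. If presence at week 12 counted alone, still more earlier infections would be included.
- **No formal conclusion rests on this endpoint.** Clinical outcomes are only described, and the error is balanced between arms in expectation. This stands and limits the consequence. The secondary anti-N non-inferiority analysis in 11.4.3 is also worded as presence by arm, so as written it does not depend on the baseline date.
- **The master protocol may settle it.** Analysis populations and visit procedures are deferred to it, and it is not among the documents. Nothing in the documents at hand resolves the conflict.

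A reader might also infer that infections in the gap are miscounted as vaccine response and so bias the non-inferiority test. The analysis text does not support this, as step 5 shows. The third sub-protocol (Protocol, section 7.1) later describes the primary outcome as a change from baseline to 12 weeks, and under that definition the sample date would matter. That is a retrospective description in another sub-protocol; section 11.4.3 is the analysis text.

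**Conclusion.** The point holds for the asymptomatic-infection endpoint and, through it, for the burden-of-disease score. Where a stored sample is used, an undocumented infection before Day 0 can be dated after randomisation. Under a constant rate and a conversion rule, about 50% of conversions would be misdated with a 12-week-old sample and 68% with a 26-week-old one. The effect is inflated counts and a dilution of any relative difference in infections, not a spurious difference between arms.

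The primary anti-S comparison and its sample size of 380 are unaffected by sample age. A headcount of affected patients would need an incidence, the proportion using stored samples and the undocumented share. The documents give none of these, so no such figure should be read from them. The weakness is moderate in consequence and cheap to remove.

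**What to change.** 1. Reconcile footnote e with the Day 0 row and section 9.2.2: require anti-S and anti-N on a sample drawn at Day 0, before the first dose, from every patient. If stored samples are kept for screening, say so and state the date from which the 6 months are counted.
2. Add an analysis rule for anyone with only a stored sample. Record its date, treat baseline serostatus as unknown, and do not count a week 12 anti-N conversion alone as a new infection; a dated PCR or antigen test after randomisation still counts.
3. Pre-specify a sensitivity analysis of the infection endpoint limited to patients with a Day 0 sample.
4. State in 11.4.3 how patients positive at baseline enter the primary analysis, so that it agrees with the description in the third sub-protocol.

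**Cost:** one extra tube for some patients, at a visit they attend for vaccination, and slightly fewer countable serological infections. The sample size stays at 380. The third sub-protocol reports this trial as already conducted, with 430 randomised. For those patients only items 2 to 4 can still be applied, and they need the sample dates and analysis wording but no new blood.
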